AF is a symptom of underlying cardiovascular risk factors and a marker of increased mortality and morbidity. We need to shift our focus to the treatment of these underlying risk factors in patients with AF. Diet, exercise, and risk factor management can be used to modify these risk factors both in the short term, and potentially with sustained effect. This study employs a randomized design to test a six-month supervised intensive exercise, diet, and risk factor management program, followed by a six-month home-based exercise and diet program. Based on previous studies, we hypothesize that this should lead to an improvement in cardiovascular risk factors, a reduction in AF burden, and possible improvements in left atrial remodeling.

3. Hypotheses:

- i) Patients with paroxysmal non-valvular AF that complete a supervised six-month program of exercise, diet, and life style modification will exhibit reduced recurrent AF and reduced cardiovascular risk factors when compared to a similar group of patients who receive usual care.
- ii) The intervention group will show improvements in physical fitness, cardiovascular risk factors, and AF symptoms and severity at both the six-month and one-year follow-up assessments compared to the usual care group.
- iii) A reduction in medication costs and emergency room visits will help offset the cost of the intervention.

4. Objectives: The objectives of this study are to demonstrate changes in symptoms and severity of AF following an exercise, diet, and risk factor modification intervention in patients with AF. Demonstrating that a comprehensive cardiac rehabilitation program is feasible and cost-effective will help us design a future larger-scale, multi-centre study.

i) Primary outcomes include:

- a. Burden of AF, including both frequency and symptoms.
 - i. The frequency of AF will be measured with 48-hour Holter monitor recording, looking at percent of time in AF at baseline, six months and one year follow up.

- ii. Symptoms of AF will be assessed using the Canadian Cardiovascular Society Severity in Atrial Fibrillation Scale (CCS-SAF) (31), and the Atrial Fibrillation Symptom Severity Scale (AFSS) (32); both are validated tools to assess burden of AF symptoms.
- iii. The 36-item Short Form Survey Instrument (33) and the EQ-5D-3L (34) will be used to measure quality of life.

ii) Secondary outcomes include:

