- a. Left atrial remodeling will be measured by LA volume index, diastolic function grade, and estimate of LA pressure via echocardiography at baseline and one year follow-up.
- b. Cardiovascular risk factors will be compared at baseline, six months and one year. These include: Systolic Blood Pressure, Hemoglobin A1C (marker of average blood sugar over 3 months), body mass index, waist circumference, and low density lipoprotein (LDL cholesterol), apnea hypopnea index (AHI), and fitness classification (metabolic equivalents (METS) achieved on exercise stress test).
- c. Using pharmanet data, total cost of all medications and specific cost for antiarrhythmic agents, antihypertensive agents, diabetes and cholesterol lowering medications will be recorded and compared at baseline and one year. Hospital Emergency visits will also be compared.

5. Methodology

5.1 Proposed Study Design: This is a parallel-group randomized controlled trial. Consecutive patients meeting eligibility criteria that are seen for routine cardiology follow-up, or those referred by family physicians, will be invited to participate in this study. Patients who accept the possibility of a year-long diet counseling and exercise program will be randomized and stratified to ‘control arm’ *versus* ‘intervention arm.’ Forty patients will be randomized to control arm and 40 patients randomized to the intervention arm. Intervention will include Phase 1, a six month program including three months of diet counseling combined with home exercise, followed by three months (starting at week 13) of an in-hospital, Cardiac rehabilitation exercise program. Phase 1 also includes risk factor management by an internist who specializes in cardiovascular risk factors. Phase 2 of the intervention will include six months of home-based maintenance exercise and diet (starting at week 25). Assuming approximately 40% of eligible patients agree to participate (based on our experience that there is a high willingness to participate in both research studies and the cardiac rehabilitation program), and given that we were able to recruit 200 research participants in one year for a previous study (35), we estimate that it is feasible to recruit a total of 80 participants over a three to six month period.

5.2 Participants: Patients will provide written, informed consent. All study procedures will be reviewed and approved by the UBC Clinical Ethics board and the VCH operational approval process.

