3. Weeks 2 to 52: Home exercise walking program: This will be recorded using a step tracker. Individual participant exercise prescription will be based on baseline exercise stress test (a modified Bruce protocol (38), supervised by cardiologist; these are a standard part of patient care and done regularly at the PI's cardiology clinic and at Richmond Hospital). Exercise stress test results provide information regarding target peak HR, METs and individual limitations. A positive stress test would be a result that would exclude a participant from the trial. The HR_{peak} will be used to prescribe target intensities during the supervised exercise component (described below). A minimum of 30 minutes five days a week of moderate aerobic activity will be the goal during the first three months of the home exercise program (participants will build towards this goal by following a structure home-based exercise plan, detailed in section 9 of ethics application "exercise prescription"). Participants will maintain a log of their daily exercise routines (included section 9, "exercise prescription").

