2. Check ins from research assistant by phone if participant's exhibit a significant reduction in physical activity detected by the step tracker. Participants will be informed that data from their step trackers will be downloaded regularly to monitor daily steps and intensity of activity (based on HR). No other data can be monitored through the step tracker. If a participant's activity drops 50% below the previous month's average over a two-week period, the research assistant will telephone the participant to ensure equipment is working properly, to discuss barriers, and to encourage them to maintain the fitness regime.
3. An optional weekly walking group will be available for participants (leaving Minoru park) to encourage adherence.

Treatment of Obstructive Sleep Apnea (OSA): This will involve the same treatment offered to the control arm (see section 5.3, above).

A six-month exercise program that begins with low-intensity exercise, followed by a three-month supervised interval training should be sufficient to effect changes in modifiable risk factors including BMI, blood pressure, and glycemic control. It should also be sufficient to lead to increased exercise capacity. A meta-analysis on cardiofit exercise programs in older adults reported an average of 23 weeks in length resulted in significant improvements in cardiorespiratory fitness (40). Months six to twelve will test the efficacy of a home-based program and investigate whether the results at six months are sustained at one year.

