5.4 Data Analysis (and sample size)

This is a parallel, randomized control study. The researcher analyzing results will be blinded to the patient's group. A statistician will be hired to analyze data and a statistician from C2E2 (UBC) has reviewed the study design. Normally distributed data will be analyzed using repeated measures analysis of variance (ANOVA) to calculate changes over time (baseline, six-months, one-year) within each group. Between groups analyses on differences from baseline will be analyzed using independent *t*-tests. Statistical significance will be set *a priori* as *p*<.05. Continuous variables will be described by group using mean (SD) (or median (P25, P75) if the data are skewed); and categorical variables will be described by frequency (percent).

To calculate effect size for the intervention group, we considered the moderate effect sizes reported in exercise studies measuring cardiorespiratory changes (e.g., Huang et al. (2016) (40) reported a moderately high effect size of 0.64 for aerobic changes following an exercise program in older adults). Using G-power software (*alpha* = .05), the

sample size required to achieve 80% power to detect an effect is 22 per group (two-tailed, or repeated measures design) (44). Based on the data from Malmo and colleagues (26) reporting a large effect size (1.0) for the difference in time spent in AF pre- and post-exercise, a sample size of less than 10 participants would achieve a power of 80%. The AF studies to-date report low attrition rates. For example, Pathak et al. (19) reported 10% attrition in the risk factor intervention group, and Malmo et al.(26) reported a 0% attrition in the three-month interval-training program. Given that the Richmond Cardiac Rehabilitation program similarly reports low drop-out rates (of approximately 2%), we have allowed for greater than 10% attrition. Including 40 participants in the intervention arm, and 40 participants in the control arm will allow for more than 10% drop out while still maintaining adequate power to detect an effect.

6. Summary and Impacts on Practice

Richmond has experience in recruiting patients with AF, cardiac rehabilitation, and bariatric diet therapy program. Our Richmond team of specialists, combined with strong partnerships with our colleagues at VGH that have experience with research trials will help guide us in implementing a successful research project.

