This study uses a reproducible intensive supervised cardiac rehabilitation program that includes exercise, diet, and risk factor modification for patients with paroxysmal, non-valvular AF. We expect that a six-month intervention will show significant improvement in fitness and weight loss and improvements in AF symptoms and frequency, and cardiovascular risk factors when compared to a control group with paroxysmal AF and similar baseline characteristics who do not receive a supervised diet and exercise program. The supervised program is followed by a six-month home-based exercise and diet program, which gives us the opportunity to look further at adherence, and whether the benefits of the six-month intensive hospital-based program can be sustained at home. A follow-up study could retest the baseline results at two years and up to five years if effects are sustained. If both the phase 1 cardiac rehabilitation and diet six-month program and phase 2 home-based program are successful, then this study could be repeated with only a home-based or community-based intervention as a lower cost alternative.

The missing piece in studies of antiarrhythmic therapy and catheter ablation for patients with paroxysmal AF is the inclusion of risk factor modification. With attention to diet, exercise, and cardiovascular risk factor modification it should be possible to obtain high rates of maintenance of normal sinus rhythm. This exercise, diet and risk factor modification model can be added to usual care or catheter ablation aiming for optimal five-year reduction in AF. Alternatively patients could be randomized to diet and exercise, versus usual care post-catheter ablation. In future trials, a loop recorder could possibly be implanted to give more accurate information of AF recurrence rates.

Future studies with longer follow up can also focus on a more robust cost benefit analysis. Demonstrating that an exercise and diet intervention is cost-effective and efficacious in reducing the burden of AF can potentially be used to encourage government funding and physicians to prescribe exercise and diet to all patients with paroxysmal AF. Ultimately a large, multi-centre trial that combines exercise, diet, and risk factor modification in patients with paroxysmal AF compared to usual care can be designed to determine whether this intervention reduces mortality, cardiac events, and stroke.

Dissemination plans:

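### Months six to twelve cannot test the efficacy of the home program, because no arm isolates Phase 2; the one-year comparison estimates the effect of the whole 12-month sequence

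*Combined protocol and SAP*

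**What the plan says.** Section 5.1 describes a two-arm parallel trial with a single allocation: "Forty patients will be randomized to control arm and 40 patients randomized to the intervention arm". Section 5.1 and the paragraph before the hypotheses give the intervention arm a fixed order. The stated purpose is to "test a six-month supervised intensive exercise, diet, and risk factor management program, followed by a six-month home-based exercise and diet program". Phase 2 begins at week 25 for those who were assigned Phase 1.

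The closing paragraph of Section 5.3.2 gives Phase 2 two aims in one sentence. The first is stated as "Months six to twelve will test the efficacy of a home-based program"; the second is to see whether the six-month results last to one year.

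Home exercise is not confined to Phase 2. Under Phase 1b, item 3 reads "Weeks 2 to 52: Home exercise walking program", and item 5 adds a home supplement in weeks 13 to 24.

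On analysis, Section 5.4 (Data Analysis) uses repeated measures ANOVA to "calculate changes over time (baseline, six-months, one-year) within each group" and independent t-tests between groups on differences from baseline. Hypothesis ii compares the arms at six months and at one year, and Section 5.4 (Data Collection) has both arms measured at those visits.

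Section 6 says that if both phases succeed, "then this study could be repeated with only a home-based or community-based intervention as a lower cost alternative". It gives no criterion for Phase 2 success.

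**The concern.** To test whether a home program works, someone comparable must go without it. Here nobody receives Phase 1 without Phase 2, and nobody receives the home program alone. Any advantage of the intervention arm at one year could come from the home program, from benefit left over from the dietitian, internist and supervised exercise of Phase 1, or from both. No planned analysis separates these sources.

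This matters beyond the one clause. The background section motivates the trial partly by the lack of studies comparing an in-hospital with a home-based program, and this design does not make that comparison. Section 6 then makes Phase 2 success part of the case for a home-only repeat, and a home program with no effect could meet that condition through carry-over.

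The second aim, whether benefit is sustained, is answerable but loosely specified. The plan names no between-arm contrast for change from six to twelve months and no rule for calling a result sustained. A non-significant within-arm change could end up being read that way.

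**Working it through.** **1. What the one-year contrast contains.** Let D6 and D12 be the between-arm differences in change from baseline at six months and one year. Then D12 − D6 = h − c, where h is the effect of Phase 2 and c is the benefit that would have been lost without it. The trial observes one number and there are two unknowns. For example, with D6 = 0.64 and D12 = 0.64, both (h = 0, c = 0) and (h = 0.32, c = 0.32) fit exactly. With D12 = 0.32, both (h = 0, c = 0.32) and (h = 0.32, c = 0.64) fit. D12 itself is still a valid randomised estimate for the complete sequence.

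**2. The plan's effect size.** Section 5.4 gives 0.64, two-tailed alpha 0.05 and 80% power, with 22 per group. A paired t-test on these inputs needs n = 21.16, rounded up to 22, so the stated figure reproduces as a within-group calculation. An independent two-sample test at 0.64 needs 39.3, that is 40 per arm. Using 0.64 as a between-arm effect below is therefore an assumption made for illustration.

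**3. Carry-over with an inert home program.** Assume D6 = 0.64 SD and h = 0, and let a share r of the six-month effect remain at one year, so D12 = 0.64 × r. The documents give no value for r, so the whole range is shown. The table gives the probability of a significant one-year result (two-sided t-test, alpha 0.05):

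| r | D12 (SD) | 40 per arm | 36 per arm |
|---|---|---|---|
| 0 | 0 | 5% | 5% |
| 0.25 | 0.16 | 11% | 10% |
| 0.50 | 0.32 | 29% | 27% |
| 0.75 | 0.48 | 56% | 52% |
| 1.00 | 0.64 | 81% | 76% |

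The 36 is 40 less 10% attrition. For r above zero, a significant result is a correct finding about the sequence. It becomes an error only when credited to the home program.

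**4. Within-arm change as evidence of maintenance.** For a paired six-to-twelve-month change, in SDs of that change, the 95% CI half-width is t(0.975, n − 1)/√n:

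- n = 40: 2.023/6.325 = 0.32
- n = 36: 2.030/6 = 0.34

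An observed mean loss just under 0.32 to 0.34 SD would be non-significant. Against 0.64, that is 0.32/0.64 = 50% to 0.34/0.64 = 53%, if the SD of the change equals the SD in which 0.64 is expressed. The documents do not give that ratio, and the percentage scales in proportion to it. The planned ANOVA may use a pooled error term, so these half-widths approximate its six-to-twelve-month comparison.

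**5. The between-arm contrast that would be added.** The half-width is t(0.975, 2n − 2) × √(2/n), again in SDs of the six-to-twelve-month change:

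- n = 40: 1.991 × 0.2236 = 0.45
- n = 36: 1.994 × 0.2357 = 0.47

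This is wider than the within-arm interval, but it removes whatever change the two arms share over the period. By step 1 it describes maintenance relative to usual care and still does not isolate h.

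**The case against.** The best defence is that the plan's main framing is maintenance. The quoted sentence goes on to ask whether six-month results last, Section 5.1 itself calls Phase 2 maintenance, and no hypothesis, objective or outcome names stand-alone efficacy of the home program. On this view the defect is one loose clause. That stands as a limit on the seriousness of the point. It does not remove it, because the clause states an aim the design cannot meet and Section 6 relies on Phase 2 success.

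Several stronger readings are tempting and are not supported:

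- *Phase 2 has no comparator.* Usual care is followed to one year and compared with the intervention arm. What is missing is a comparator that isolates Phase 2.
- *Nothing planned can address whether benefit is sustained.* The one-year between-arm comparison is planned and bears on it directly. Only the six-to-twelve-month contrast and a rule for interpretation are missing.
- *A home program would be adopted on these results.* Section 6 speaks of repeating the study, and a home-only randomised repeat would supply the missing comparison. The risk lies in what is taken as evidence for that repeat.
- *Season or a particular rate of decay explains the results.* The documents give no figures for either, and the arms are followed over the same intervals.
- *A non-significant change within the arm could hide a loss of about 70%.* The figure 0.45/0.64 = 70% belongs to the between-arm contrast. The within-arm figure is 50 to 53%, on the equal-SD assumption.

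**Conclusion.** The stated efficacy aim for months six to twelve cannot be met, and this follows from the allocation and the phase schedule without any numerical assumption. The one-year between-arm difference is a valid estimate of the 12-month sequence against usual care, carry-over included. The point invalidates no planned between-arm test, primary outcome or sample size.

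The size of possible misattribution depends on assumptions. With a 0.64 SD between-arm effect at six months and an inert home program, the chance of a significant one-year result runs from 5% with no carry-over to 81% with full carry-over at 40 per arm. On maintenance, a non-significant within-arm change is weak evidence, with a half-width of 0.32 to 0.34 SD of that change. The change should be made because it alters what the trial may conclude and uses data already planned.

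**What to change.** 1. In the closing paragraph of Section 5.3.2, replace the efficacy claim with wording such as: *The one-year comparison estimates the effect of the complete 12-month strategy (supervised phase, then home maintenance) versus usual care and describes maintenance after supervision. It does not estimate the efficacy of the home program on its own.*
2. In Section 5.4 (Data Analysis), judge whether benefit is sustained by the planned between-arm difference at one year. Report with it the between-arm difference in six-to-twelve-month change and its 95% CI, for outcomes measured at both visits. Echocardiography is excluded, since it is done only at baseline and one year. State that within-arm ANOVA and a non-significant change will not be used for this judgement.
3. In Section 6, state that one-year results inform maintenance after supervision and are not evidence that a home-only program works, which would need its own randomised comparison.

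The cost is a narrower claim about Phase 2 and one extra contrast, with no new data. Re-randomising Phase 1 completers to home program or none is not proposed. At 0.64 SD it would have 51% power with 20:20 and 46% with 18:18, and 80% power would need 40 per group, that is 80 completers against 40 planned in the arm.

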5.4 Data Collection

All measurements (save demographics and medical history) will be collected at baseline, six months, and one year in both groups.

1. Patient demographics: age, sex, ethnicity, education, income, and living situation.
2. Medical history: medications and cost; hospital emergency visit and admission < 1yr, known coronary artery disease defined by prior myocardial infarction or presence of 50% stenosis on CT or invasive angiogram; admission for heart failure, prior stroke; average daily glasses of alcohol, smoking status (including frequency and amount); the Canadian Cardiovascular Society Severity in Atrial Fibrillation (CCS-SAF) Scale, (31) the Atrial Fibrillation Symptom Severity Scale (AFSS) (32), the 36-item Short Form Survey Instrument (33) and the EQ-5D-3L (34).
3. Anthropometrics: Body mass index (BMI), waist circumference, neck circumference, modified mallampati score (41) and blood pressure.
4. Blood work: Hemoglobin AIC, total cholesterol, creatinine, low-density lipoprotein, high-density lipoprotein, triglycerides, ALT, c-reactive protein, electrolytes, and brain natriuretic peptide.
5. Level 3 home sleep study: Apnea-hypopnea index, minimum saturation, and time spent with saturation < 90%, Epworth Sleepiness Scale (42).
6. Godin's leisure time physical activity measure will be used measure baseline physical activity levels (43).
7. Exercise Stress Test at maximal effort: Maximum METs achieved, peak heart rate, and rating of perceived exertion.
8. 48-hour Holter monitor: 48-hour heart rhythm monitor to determine frequency and duration of AF measured as the percent of time in AF.
9. Echocardiography at base line and one year: measurements: LA volume, LA pressure, diastolic function, grade, calculated biplane LVEF, and left ventricular hypertrophy.

All data sheets are attached in section 9 of the application. There is a data sheet for each: sleep study, echo, blood work, stress test, physical exam, and Holter monitor.

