Richmond Hospital has successfully run a Cardiac Rehabilitation program for over 20 years. The 8-week program includes supervised exercise sessions (two per week), in conjunction with diet and stress management classes (one each per week). The program has reported low voluntary dropout rates (e.g., two dropouts of 100 patients in the last six months of the program). At present, cardiologists do not typically refer patients with AF to cardiac rehabilitation. For the current project, during the first six months (Phase 1) we plan to extend the duration of the existing Cardiac Rehabilitation exercise program to three months and we plan to use moderate to high intensity interval training combined with resistance exercises as per current literature in exercise and patients with AF. In addition, study participants will receive a heart rate and step tracker to guide intensity and duration for a home-based walking program and will maintain a minimum of 10 to 20 minutes of total body resistance training at home.

Richmond also has a successful bariatric surgery program where 200 patients per year are treated first with diet therapy, followed by mainly laparoscopic sleeve gastrectomy. Similar to the Legacy study described above, we will enroll participants with BMI greater than or equal to 27 kg/m^2 in a diet intervention run by dietitians from the Richmond Bariatric program. The goal of the nutrition component will be to reduce total body weight by at least 10%. The diet intervention will be an individualized, healthy diet program promoting reduced carbohydrate content, smaller portions, and mindful eating (30). During months six to twelve of the intervention (Phase 2), participants will continue with a home-based aerobic exercise program combined with resistance training that was learned in the hospital cardiac rehabilitation program. Participants will monitor their sessions using the heart rate and step tracker along with self-reported exercise logs. Motivated participants are free to join a community gym. The individual exit diet counseling will encourage participants to follow the final diet prescribed.

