4. Week 13 to 24: Three-month Cardiac Rehabilitation Program at Richmond hospital: Participants will exercise for one hour twice weekly at Richmond Hospital Cardiac Rehabilitation Centre. Participants can choose a cohort that participates in am or evening and or weekend classes to accommodate work schedules. Participants will exercise using a combination of aerobic – interval training following methods informed by Malmo's (26) study, combined with whole body resistance training using an elastic band (Theraband®). Details regarding exercise prescription are shown in section 9 of the ethics application. There will be a maximum of 10 participants per exercise session with two instructors. For the first two weeks, three additional research assistants will be present to ensure a 2:1 ratio of participants to study team member. Having additional facilitators will help participants become familiar with the equipment and will make the interval transitions easier to manage during those first four classes. After this orientation phase, participants should be able to manage their intervals with less assistance and two trained cardiac rehabilitation experts should be sufficient. The aerobic machines are state of the art and exercise prescription (target heart rates and workload) will be based on initial cardiologist-supervised baseline exercise test, personal limitations, and progress during home program. A nurse and physiotherapist trained in cardiac rehabilitation will supervise patients. Staff will monitor blood pressure, heart rate, and rating of perceived exertion (using Borg's 10-point scale) at each session in addition to weekly body weights in order to ensure participants are meeting target exercise intensities (data sheet in section 9 of ethics application).
5. Week 13-24: Home-based exercise program supplement. In addition to the in-hospital, supervised exercise program, participants will be prescribed individualized home exercise regimes. These will increase incrementally as the participants proceed through the program. Participants will maintain a log of their daily exercise routines and track steps and heart rate with a step tracker.

Phase 2: Intervention Arm: Six month home-based diet and exercise program (weeks 25-52) will include:

1. Home based with step/activity tracker to track steps and HR (along with participant exercise log).

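### The plan describes no adverse-event collection and no by-arm safety comparison, and its text conflicts on whether emergency visits and admissions are collected during follow-up

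*Combined protocol and SAP*

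**What the plan says.** For the exercise program, the background section states that "we plan to use moderate to high intensity interval training combined with resistance exercises". It also sets a weight-loss goal of at least 10%.

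The hypotheses and outcomes in sections 3 and 4 concern AF burden, symptoms, quality of life, left atrial remodeling, risk factors, fitness and cost. None is framed as a harm. The one event-type comparison closes the medication-cost item, section 4.ii.c: "Hospital Emergency visits will also be compared". No data source or time window is given for it.

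Section 5.4 Data Collection sets out nine groups of data. Emergency visits, hospital admissions, heart-failure admission and prior stroke appear only in item 2, medical history. The opening sentence of that section excludes demographics and medical history from the measurements repeated at six months and one year. On forms, it says "All data sheets are attached in section 9 of the application" and then "There is a data sheet for each: sleep study, echo, blood work, stress test, physical exam, and Holter monitor".

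Two further records are mentioned in section 5.3.2. At rehabilitation sessions, "Staff will monitor blood pressure, heart rate, and rating of perceived exertion", with weekly weights, "in order to ensure participants are meeting target exercise intensities (data sheet in section 9 of ethics application"). For home exercise, "Participants will maintain a log of their daily exercise routines (included section 9"). Both belong to the program arm.

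The Data Analysis section, also numbered 5.4, plans no safety summary.

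**The concern.** A trial of an intensive exercise and diet program in patients with AF and comorbidity needs to set harms beside benefits. As described, a fall, an injury, syncope, a death, or an arrhythmia outside the 48-hour Holter recording has no stated route into the results of either arm. The events that are listed have uncertain follow-up collection.

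Analysts cannot repair this afterwards. Events not asked about during the year cannot be recovered evenly in the two arms. Those noticed informally would come mostly from the arm that staff see most often, so a later comparison would be biased against the program or impossible to interpret.

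The results are meant to help design a larger trial (section 4). Section 6 also foresees that evidence of this kind might help encourage "physicians to prescribe exercise and diet to all patients with paroxysmal AF". Both uses call for harm counts by arm.

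**Working it through.** The plan states no figure on harm, so there is none to reproduce. The check has three parts.

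**1. Does the plan collect events after baseline?**

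- Section 4.ii.c compares emergency visits between arms, which requires follow-up data.
- Section 5.4 Data Collection, item 2, is the only place where emergency visits, admissions, heart-failure admission and stroke are listed, and that item is exempt from collection at six months and one year.
- The same item holds CCS-SAF, AFSS, SF-36, EQ-5D-3L and medication cost. Taken literally, the exemption would also remove the follow-up symptom and quality-of-life data that the primary outcomes need.

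The exemption is therefore probably loose drafting, but the text does not say which of the listed items are repeated. Section 4.ii.c and section 5.4 cannot both be followed as written.

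**2. Is staff contact equal in the two arms?**

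Scheduled program-arm contacts from section 5.3.2, assuming one nutrition class a week and full attendance:

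- Week 1: dietitian consult and exercise intake = 2
- Weeks 2 to 13: 12 classes
- Weeks 13 to 24: 2 sessions × 12 weeks = 24
- Week 24: final dietitian consult = 1
- Total: 2 + 12 + 24 + 1 = 39, not counting internist visits

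Section 5.3.1 gives controls usual follow-up by their own physicians and no scheduled program sessions. In weeks 25 to 52 the gap narrows: program participants have an optional walking group, and telephone calls only when tracked activity falls.

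**3. What could 40 per arm show if events were collected?**

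Inputs from the plan: 40 per arm; two sessions a week in weeks 13 to 24. The 36 is 40 × 0.90, that is, 10% dropout. The documents give no event rates, so those below are assumptions.

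- Supervised exposure at full attendance: 40 × 2 × 12 = 960 person-sessions.
- Chance of at least one affected participant among 40, 1 − (1 − p)^40: 33% at p = 1%, 55% at 2%, 87% at 5%, 98.5% at 10%.
- Zero events, one-sided 95% upper bound, 1 − 0.05^(1/n): 7.2% for n = 40 and 8.0% for n = 36.
- Zero events, upper limit of the exact two-sided 95% interval, 1 − 0.025^(1/n): 8.8% for n = 40 and 9.7% for n = 36.
- Power to distinguish 5% from 20% with 40 per arm: about 53%.

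A by-arm table would therefore be descriptive. These figures show what collection would buy; they do not measure the size of the gap.

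**The case against.** The strongest reply is that the forms are held in section 9 of the ethics application, which was not available. A reader might infer from the six named sheets that no adverse-event form exists. The documents do not support that. The session data sheet and the exercise log are outside the six, and so are the symptom and quality-of-life questionnaires, which the trial plainly uses. The list is not closed.

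A reader might also infer that the trial can report no harm by arm at all. That is too strong. Emergency visits are to be compared. Holter AF time, blood pressure, creatinine, ALT, electrolytes, natriuretic peptide and stress-test results are measured in both arms at all three times, and ejection fraction at baseline and one year. The symptom scales are also meant to be compared over time. Any of these could worsen in one arm.

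Finally, section 6 offers wide prescription only as a possible use, in a paragraph that looks ahead to longer and larger studies. It is not a claim that this trial will settle the matter.

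All three replies stand, but they leave the main point intact. Mean changes in measurements do not record discrete events such as falls, syncope or deaths. The session sheet is described as a check on exercise intensity and exists in one arm only. Even if a reporting form exists in the application, this plan names no harm outcome and no analysis of one.

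**Conclusion.** The point holds in this form: the available text describes no adverse-event collection and no by-arm safety comparison. The one event-type comparison it plans, emergency visits, rests on data whose follow-up collection the plan itself leaves in conflict. Ascertainment of anything noted informally would be unequal, mainly in weeks 1 to 24.

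The documents do not show that no event form exists, or that no worsening could be seen by arm.

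The gap should be closed because lost events cannot be reconstructed evenly. The information gained would be limited. A harm affecting 5% of an arm of 40 would probably appear at least once (87%), but uncommon harms could not be ruled out. Those figures rest on assumed rates and full follow-up of 40.

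**What to change.** 1. Reconcile section 4.ii.c with section 5.4 Data Collection, so that emergency visits, admissions, heart failure and stroke are stated as collected at six months and one year in both arms. State also which other items in the medical-history group are repeated.
2. Add one event form with identical questions in both arms at those two existing visits. Besides the events in step 1, it should cover death, syncope, fall or injury, and any event needing medical care, with date and seriousness. Define adverse and serious events. For deaths and missed visits, add a route that is the same in both arms, such as a record check or a telephone call. If section 9 of the ethics application already holds a suitable form, cite it.
3. Keep events noted at rehabilitation sessions on a separate program-arm log, outside the between-arm comparison.
4. Add to section 4.ii the number of participants with at least one event and with at least one serious event, by arm, with exact 95% confidence intervals, labelled as descriptive.

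The cost is one form, a check for deaths and missed visits, one table and an ethics amendment. Sample size, treatment and visit schedule do not change. The form should be in place before the first six-month visit. The report must say that 40 per arm cannot exclude uncommon harms.
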